2.4.1 Randomized Trials of Elective Induction at Term versus Expectant Management

There have been several small randomized clinical trials comparing elective induction of labor at 37-40 weeks' gestation with expectant management until 41-42 weeks (Table 3).³⁷⁻⁴² None of these studies found an increased frequency of cesarean section among induced participants. However, these trials have significant limitations. First, all were underpowered to detect the magnitude of increase in cesarean rate that would be considered clinically relevant. In addition, because two trials only included women with a favorable Bishop score, the generalizability of the data to women with an unfavorable score is limited.

Nevertheless, meta-analysis of these data generated by randomized trials reveals a reduction in the frequency of cesarean section with induction (RR 0.89; 95% CI 0.81 to 0.97).² Although it did not address elective induction, the Hypertension and Pre-eclampsia Intervention Trial At Term (HYPITAT), a randomized trial comparing induction to expectant management for women with hypertensive disease of pregnancy, also demonstrates that labor induction may not increase the risk of cesarean (14% in the induction of labor group versus 19% in the expectant management group (RR 0.75; 95% CI 0.55-1.04).⁴³

2.5 Rationale for a Randomized Clinical Trial

Given the reported increased risks of adverse events in pregnancies extending beyond 39 weeks it has been hypothesized that a policy of planned elective induction at 39 weeks could improve outcomes for the infant and the mother. For multiparous patients, especially those with a favorable cervix, it is perhaps easy to justify an elective induction at 39 weeks given the low risk of cesarean section. However, for nulliparous patients the current evidence, derived mainly from retrospective observational studies, does not allow a clear recommendation. Nevertheless, a trend towards an increased rate of elective labor induction in pregnancies at 39 weeks has been reported, indicating that practitioners are more commonly using elective induction at this gestational age,⁴³ even as others caution against routine elective induction prior to 41 weeks given the reported increased risk of cesarean delivery.^{19,44,45,46} Ultimately, a randomized controlled trial is necessary to satisfactorily understand whether elective induction of labor of nulliparas at 39 weeks improves neonatal and maternal outcomes.

3 Study Design

3.1 Primary Research Question

This randomized trial will address the primary research question: does elective induction of labor in nulliparous women at 39 weeks improve perinatal outcome compared with expectant management?

3.2 Secondary Research Questions

Secondary research questions this study will address are:

- Does elective induction of labor in nulliparous women at 39 weeks reduce the risk of any of the maternal outcomes listed in Section 4.7.2?
- Does elective induction of labor in nulliparous women at 39 weeks reduce the risk of any of the fetal and neonatal outcomes listed in section 4.7.3?
- Does elective induction of labor in nulliparous women at 39 weeks modify the utilization of the medical resources listed in section 4.7.4?
- If the two groups show a difference in the incidence of the primary outcome or cesarean, does the proposed effect of elective induction of labor in nulliparous women at 39 weeks vary according to any of the subgroups listed in section 5.5?

3.3 Design Summary

The study is a randomized controlled multi-center clinical trial of 6000 women at 38 weeks 0 days to 38 weeks 6 days randomized to one of two arms at participating MFMU Network clinical centers.

- Elective induction of labor between 39 weeks 0 days and 39 weeks 4 days
- Expectant management (unless a medical indication arises) until at least 40 weeks 5 days.

3.4 Eligibility Criteria

3.4.1 Inclusion Criteria

1. Nulliparous - no previous pregnancy beyond 20 weeks
2. Singleton gestation. Twin gestation reduced to singleton, either spontaneously or therapeutically, is not eligible unless the reduction occurred before 14 weeks project gestational age (see below).
3. Gestational age at randomization between 38 weeks 0 days and 38 weeks 6 days inclusive based on clinical information and evaluation of the earliest ultrasound as described in Gestational Age Determination in Section 3.4.2 below.

3.4.2 Gestational Age Determination

Gestational age is determined using criteria proposed by the American Congress of Obstetricians and Gynecologists, the American Institute of Ultrasound in Medicine and the Society for Maternal-Fetal Medicine⁴⁷ and is denoted “project gestational age”. The “project EDC”, which is based on the project gestational age, cannot be revised once a determination has been made. If the pregnancy is conceived by in-vitro fertilization, project gestational age is calculated from the date of embryo transfer and the embryo age at transfer. If the pregnancy is conceived spontaneously (including ovulation induction and artificial

insemination) information from the earliest dating ultrasound and the last menstrual period are used to determine project gestational age. The following algorithm is used:

- The first day of the last menstrual period (LMP) is determined, and a judgment made as to whether or not the patient has a “sure” LMP date.
- If the LMP date is unsure, measurement(s) obtained at the patient’s first dating ultrasound examination is used to determine the project gestational age. The first dating ultrasound must have been conducted before 14 weeks 0 days by crown rump length (CRL).
- If the LMP date is sure, project gestational age is determined by a comparison between the gestational age by LMP and by the earliest dating ultrasound. The first dating ultrasound must have been conducted before 21 weeks 0 days by LMP. If the ultrasound confirms the gestational age by LMP as in the table below, the LMP-derived gestational age is used to determine the project gestational age. Otherwise, project gestational age will be determined based upon the ultrasound measurement.

Table 4. Cutoffs for Using LMP to Determine Gestational Age for Sure LMP

Gestational age at first ultrasound by LMP	Ultrasound method of measurement	Ultrasound agreement with LMP
Up to 8 weeks 6 days	CRL	± 5 days
9 weeks 0 days to 13 weeks 6 days	CRL	± 7 days
14 weeks 0 days to 15 weeks 6 days	Per institution	± 7 days
16 weeks 0 days to 20 weeks 6 days	Per institution	± 10 days

3.4.3 Exclusion Criteria

1. Project gestational age at date of first ultrasound is > 20 weeks 6 days
2. Plan for induction of labor prior to 40 weeks 5 days
3. Plan for cesarean delivery or contraindication to labor
4. Breech presentation
5. Signs of labor (regular painful contractions with cervical change)
6. Fetal demise or known major fetal anomaly
7. Heparin or low-molecular weight heparin during the current pregnancy
8. Placenta previa, accreta, vasa previa
9. Active vaginal bleeding greater than bloody show
10. Ruptured membranes
11. Cerclage in current pregnancy
12. Known oligohydramnios, defined as AFI < 5 or MVP < 2
13. Fetal growth restriction, defined as EFW < 10th percentile
14. Known HIV positivity because of modified delivery plan

15. Major maternal medical illness associated with increased risk for adverse pregnancy outcome (for example, any diabetes mellitus, lupus, any hypertensive disorder, cardiac disease, renal insufficiency)
16. Refusal of blood products
17. Participation in another interventional study that influences management of labor at delivery or perinatal morbidity or mortality
18. Delivery planned elsewhere at a non-Network site

3.5 Informed Consent Criteria

Each center will develop its own consent forms according to the requirements of its own institutional review board using the model consent form in Appendix B. Each center will also develop its own patient research authorization documents, as required by the HIPAA Privacy Rule, following the guidelines of its own institution. A copy of the signed consent form will be provided to the patient.

Women who are not fluent in English will be enrolled by a person fluent in their language. Both verbal and written informed consent and authorization will be obtained in that language; if this is not possible the patient will be excluded.

3.6 Randomization Method

Randomization for consenting women will occur at 38 weeks 0 days to 38 weeks 6 days of gestation. Consenting women will be assigned to induction of labor at 39 weeks 0 days to 39 weeks 4 days or expectant management in a 1:1 ratio according to a randomization sequence prepared and maintained centrally by the Biostatistical Coordinating Center (BCC).

The simple urn method will be used to generate the randomization sequences because it provides a high probability of balance in treatment assignments, it is unpredictable, and it allows an explicit randomization analysis to be conducted with relative ease.⁴⁸ Randomization will be stratified by clinical site to assure balance between the two treatment groups with respect to anticipated differences in the clinic populations and possible differences in patient management.

4 Study Procedures

4.1 Screening for Eligibility and Consent

All nulliparous women with a singleton gestation between 34 and 38 weeks are potentially eligible for screening. Inclusion/exclusion criteria will be reviewed with the patient's chart.

If a patient appears to meet the criteria for the trial, she will be told about the study and asked for written informed consent to participate in the trial. Consent may be obtained anytime from 34 weeks 0 days to 38 weeks 6 days of gestation.

Each patient must undergo a digital cervical exam between 72 hours prior to randomization and 24 hours after randomization. The three components of the modified Bishop score must be obtained during this exam. Table 5 provides the scoring system that uses the following three components to derive the modified Bishop score:

- Cervical dilation
- Cervical length or effacement
- Fetal station

Table 5. Scoring System for the Modified Bishop Score

Station (in relation to the spines)	-3 cm	-2 cm	-1 - 0 cm	1 - 2 cm
	0	1	2	3
Dilation (of the cervix)	0 cm	1-2 cm	3-4 cm	>4 cm
	0	2	4	6
Length (of the cervix)	3 cm	2 cm	1 cm	0 cm
	0	1	2	3

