4.2 Randomization

Eligibility should be verified again before randomization. Eligible and consenting patients will be randomized by certified research staff using an internet based randomization system maintained by the BCC. Randomization will occur when the patient is from 38 weeks 0 days to 38 weeks 6 days of gestation. The patient will be assigned either to the induction of labor group or the expectant management group.

If the patient has had a digital cervical exam within the past 72 hours, and all components of the modified Bishop score are documented (cervical dilation, cervical effacement or cervical length, and fetal station), randomization may be done in person or over the telephone. If the patient has not had a digital cervical exam within the past 72 hours, or if components of the modified Bishop score are not documented, she must be randomized in person and have a digital cervical exam within that same day.

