4.3 Baseline Procedures

In addition to information collected for eligibility, project gestational age, and project EDC determination, the following information will be obtained at randomization from a patient interview followed by a review of her chart:

- Components of the modified Bishop score: cervical dilation, cervical length or effacement, and fetal station from digital cervical exam
- Demographic information: age, race, ethnicity, insurance status
- Medical history: first clinic weight, current weight, height, chronic disease history
- Obstetrical history including outcome(s) of any prior pregnancies
- Social history: marital status, alcohol use, and tobacco use
- Current pregnancy complications

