5.5 Analysis Plan

All statistical analyses will be based upon the total cohort of patients randomized into the trial. Although data on some patients may be missing, all relevant data available from each patient will be employed in the analyses. Patients will be included in the treatment group to which they were randomly assigned regardless of compliance.

The primary analysis will consist of a simple comparison of binomial proportions. The relative risk and confidence interval will be reported. The individual components of the composite outcome will also be examined. If the treatment groups are found to differ on a pre-treatment factor known to be a risk factor for the outcome, the statistical analysis will adjust for these differences. An evaluation of treatment by center interaction will be included. An analysis adjusting by center also will be performed to ensure that center differences do not change the conclusion.

If the two groups show a difference in the incidence of the primary outcome or cesarean, interactions will be evaluated and subgroup analyses conducted to determine whether the effect prevails throughout

particular subgroups of patients. Indeed, NIH guidelines require investigators to evaluate consistency between the genders and across racial subgroups (see Section 5.5.1). It should be noted, however, that subgroup analyses have been greatly abused, particularly when there is no overall treatment difference.⁵² There is a strong temptation to search for a specific subpopulation in which the therapy is nevertheless effective. Yusuf et al. concluded “*the overall ‘average’ result of a randomized clinical trial is usually a more reliable estimate of the treatment effect in the various subgroups examined than are the observed effects in individual subgroups.*”⁵³ Thus subgroup analyses will be interpreted with care.

It is generally acknowledged that subgroup analysis that is pre-specified in the protocol has more validity than ad-hoc comparisons. The following factors will be considered for subgroup analysis, if there is a significant interaction between the factor of interest and the treatment effect.

- Race/ethnicity (see below)
- Modified Bishop score (< 5 and ≥ 5)
- Body mass index (obese and non-obese)
- Maternal age (< 35 and ≥ 35 years)
- Admitting provider specialty (see below)

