6.1 Data Collection Forms

Data will be collected on standardized forms on which nearly all responses have been pre-coded. Each form is briefly described below:

- AR01 Screening Log.
- AR02 Eligibility and Randomization Form is completed for all patients eligible and consenting for the study, and documents the project gestational age and randomization digital cervical exam.
- AR04 Baseline Form is completed for all randomized patients. This form includes detailed demographic and social data, and medical and obstetrical history.
- AR05 Clinic and Hospital Visit Log documents scheduled and unscheduled clinic, urgent care and hospital visits, procedures and diagnostic tests, including the antepartum portion of the delivery admission.
- AR08 Labor and Delivery Summary Form documents specific pregnancy complications since randomization, in addition to labor, delivery and postpartum information.
- AR08A Labour Agency Questionnaire
- AR09 Neonatal Baseline Form records date and time of birth, delivery data and status at delivery, for each fetus/infant.
- AR10 Neonatal Outcome Form records outcome data for all infants admitted to the NICU or special care nursery.
- AR11 Patient Status Form documents loss to follow up/withdrawal status, last date of contact for lost to follow-up patients.
- AR12 Adverse Event Form records serious and non-serious adverse events.
- AR13 Postpartum Follow-up Form
- AR13A Maternal Follow-up Log documents the reasons and diagnoses associated with maternal clinic, urgent care and hospital visits
- AR13B Infant Follow-up Log documents the reasons and diagnoses associated with infant clinic, urgent care and hospital visits

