
ORGANIZATION
 
Clinical Centers: UAB, Ohio State, UTSW, Utah, Brown, Columbia, Case Western, UT-Houston, UNC, Northwestern, UTMB-Galveston, Colorado, Duke, Stanford, Magee, U Penn
 
Subcommittee: [name] (Chair)
 
DESIGN
 
Major Eligibility Criteria:
 
 ❖ Singleton gestation ❖ Gestational age 38⁰ to 38⁶ wks ❖ Nulliparous 
Groups:
 
 ❖ Induction of labor at 39 weeks ❖ Expectant management with induction by 42 weeks, if undelivered 
Random Allocation: Standard urn design; 1:1 allocation
 
Level of Masking: Unmasked
 
Stratification: 
 ❖ Clinical site 
 
Sample Size: 
 ❖ 6000 
 
Assumptions: 
 ❖ Outcome event=perinatal death /neonatal adverse outcome ❖ Expectant management event rate = 3.5% ❖ Induction of labor group event rate = 2.28% (38% reduction) ❖ Type 1 error = 5% two sided ❖ Power =85% 
 
Interim Analysis: 
 ❖ Lan-DeMets group sequential method 
	
SCHEDULED EVALUATIONS / DATA COLLECTION
 
Randomization: 
 ❖ Gestational age estimation ❖ Digital cervical exam; Bishop score ❖ Pregnancy, exposure and medical history 
 
Post-randomization: 
 ❖ Weekly visit with provider (expectant management group) 
 
Delivery: 
 ❖ Patient-centered outcomes questionnaire ❖ Delivery and neonatal data ❖ Central chart review for primary outcome 
 
Postpartum: 
 ❖ Patient-centered outcomes questionnaire 
 
MANAGEMENT PROTOCOL
 
Induction Group 
 ❖ Induction via oxytocin at 39⁰-39⁴ wks. ❖ If unfavorable cervix (modified Bishop score < 5) start with cervical ripening 
 
Expectant Mgmt Group 
 ❖ Continue pregnancy until at least 40⁵ wks (unless indication for delivery) ❖ Start antepartum fetal testing no later than 41⁶ ❖ All patients induced by 42² wks 
 
OUTCOME MEASURES
 
Primary: 
 ❖ Neonatal adverse outcome/fetal death 
 
Major Secondary: 
 ❖ Cesarean delivery ❖ Maternal adverse outcomes ❖ Gestational age at delivery ❖ Utilization of medical resources 
 
TIMETABLE (as originally planned)
 
Enrollment 
 ❖ Oct 2013 to Sep 2016 
 
Data Collection 
 ❖ Oct 2013 to Nov 2016 
 
Closeout 
 ❖ Dec 2016 to Mar 2017 
 
TIMETABLE (revised)
 
 ❖ Oct 2013 to Oct 2017 ❖ Oct 2013 to Dec 2017 ❖ Jan 2018 to Apr 2018

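### The cervical exam behind the Bishop-score subgroup may follow an unmasked assignment, so some women could be classified with knowledge of their arm

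*Combined protocol and SAP*

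**What the plan says.** Section 4.1 sets the exam window: "Each patient must undergo a digital cervical exam between 72 hours prior to randomization and 24 hours after randomization". The exam supplies dilation, length or effacement, and station, which make up the modified Bishop score.

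Section 4.2 covers a woman with no complete exam in the previous 72 hours: "she must be randomized in person and have a digital cervical exam within that same day". It does not say whether the exam or the assignment comes first.

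Elsewhere the score is handled as a baseline measure. Section 4.3 lists its components among the baseline items, under the statement that "the following information will be obtained at randomization from a patient interview followed by a review of her chart". In section 6.1, form AR02 is the one that "documents the project gestational age and randomization digital cervical exam".

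Section 5.5 lists five candidate subgroup factors, one of them "Modified Bishop score (< 5 and ≥ 5"). Section 3.2 makes subgroup variation a secondary question, and a conditional one: "If the two groups show a difference in the incidence of the primary outcome or cesarean, does the proposed effect of elective induction" of labor vary by subgroup? Section 5.5 then also requires a significant interaction.

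Appendix A gives "Level of Masking: Unmasked".

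**The concern.** A subgroup factor should be fixed before allocation, or at least be beyond the influence of allocation. Here a stated rule lets the factor be measured up to 24 hours after an open assignment. The three components are graded by hand into coarse categories. In Table 5 one step in dilation is worth 2 points, which can be enough to cross the cut at 5. If an examiner who knows the arm grades borderline women differently in one arm, the favorable and unfavorable groups are no longer defined in the same way in both arms. A false difference in effect between them could follow.

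The plan acknowledges a comparable issue for another factor. Section 5.5.2 says openly that admitting provider specialty is not measured at baseline. It gives no such warning for the Bishop score, and it plans no analysis limited to exams done before randomization.

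There is one route beyond the subgroup. Section 5.5 provides for adjustment when the arms differ on a pre-treatment risk factor. If the Bishop score were used in that way, scores recorded after allocation would bring the same problem into the adjusted analysis, and arm-dependent scoring could itself create the imbalance that prompts the adjustment.

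**Working it through.** **Reading the rules together.** Section 4.1 allows exams up to 24 hours after randomization. Section 4.2 allows a same-day exam in either order. The two limits differ, and neither puts the exam before the assignment. Appendix A rules out masking, and no section assigns the exam to someone unaware of the arm. So a score recorded with the arm known is permitted. Such exams can arise only in women without a complete exam in the prior 72 hours. This is the only Bishop score that the protocol says is collected, so I infer that it defines the subgroup.

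**Scale.** The plan has no figure to reproduce on this point. The following is an illustration under no true treatment effect.

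Inputs from the documents: 3000 women per arm (5.2.1); cesarean 20% with a favorable and 34% with an unfavorable cervix (the expectantly managed women in the observational study in 2.4).

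Assumptions: half of each arm has an unfavorable cervix (1500 and 1500); a share of exams is late; in the induction arm only, some favorable women are recorded as unfavorable.

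With k women moved, each with cesarean risk r, the induction-arm rates are:
- unfavorable: (1500 × 0.34 + k × r) / (1500 + k)
- favorable: (1500 × 0.20 − k × r) / (1500 − k)

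Each is divided by the expectant-arm rate, 0.34 or 0.20.

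| Late exams; share of them shifted | k | r | Unfavorable: rate, false RR | Favorable: rate, false RR |
|---|---|---|---|---|
| 20%; 10% | 60 | 0.20 | 522/1560 = 33.5%, 0.98 | 288/1440 = 20.0%, 1.00 |
| 50%; 20% | 300 | 0.20 | 570/1800 = 31.7%, 0.93 | 240/1200 = 20.0%, 1.00 |
| 20%; 10% | 60 | 0.27 | 526.2/1560 = 33.7%, 0.99 | 283.8/1440 = 19.7%, 0.99 |
| 50%; 20% | 300 | 0.27 | 591/1800 = 32.8%, 0.97 | 219/1200 = 18.3%, 0.91 |

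Here k = 3000 × late share × shifted share. The rows with r = 0.27 give the moved women the midpoint of 20% and 34%, which is more plausible for women near the cut. Part of the distortion then moves into the favorable group. In every row the overall induction-arm rate stays at 810/3000 = 27%.

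**Chance of a false interaction.** I used a two-sided 5% Wald test on the difference of log relative risks, with variance equal to the sum of (1 − p)/(n × p) over the four cells. The chance is 5.4% and 12.0% in the first two rows and 5.1% and 9.3% in the last two, against a nominal 5%.

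**Opposite direction.** Suppose instead that truly unfavorable women in the induction arm are recorded as favorable and keep their 34% risk, with 50% to 70% truly unfavorable. The false RR in the favorable group is then:
- 1.01 to 1.02 with 10% of exams late and 10% of those women misrecorded;
- 1.03 to 1.07 with 25% late and 20% misrecorded;
- 1.06 to 1.13 with 50% late and 20% misrecorded.

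The chance of a significant interaction, tested on the risk-difference scale, is 5.0% to 5.2%, 6.0% to 9.4% and 8.6% to 20%. The log-RR test gives somewhat more in the last case, 11% to 25%.

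**The case against.** The case for leaving this alone is substantial. The same-day rule in 4.2 is equally met by examining first. Section 4.2 has certified research staff randomize, and no section says who examines or what that person has been told. The manual of operations, which was not available here, may fix the order. The subgroup is one of five, needs both an overall difference and a significant interaction, and is to be interpreted with care under 5.5. The late-exam shares above have no source. The shifts are large and all one way: 60 of 300, or 20%, and 300 of 750, or 40%, of the favorable late-examined women in one arm. All of this stands. It limits the point but does not remove it, because 4.1 expressly permits an exam after randomization.

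A reader might infer more than the documents support:

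- **That the examiner knows the arm.** The text supports only that the examiner could know it.
- **That ineligible women will be found only after allocation.** The exclusion reads "Signs of labor (regular painful contractions with cervical change"), so it also needs contractions, which can be recognized without this exam. Section 4.2 has eligibility verified again before randomization.
- **That scores will be missing more often in the expectant arm.** The exam is mandatory and these women attend in person, so this is conjecture.
- **That the ripening rule gives a motive for biased scoring.** Section 4.4 uses the same cut, but induction falls 1 to 11 days after randomization (38 weeks 6 days to 39 weeks 0 days at the shortest, 38 weeks 0 days to 39 weeks 4 days at the longest). No section says that the randomization exam decides ripening. The direction of any bias is unknown.
- **That the distortion amounts to half of the 15% cesarean effect in 5.2.2.** That effect is an overall one, and reclassifying women between subgroups cannot alter it.

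**Conclusion.** The point holds in a limited form. The protocol permits the score that defines a pre-specified subgroup to be recorded after an unmasked assignment, and some women may be misclassified as a result. The comparisons of the primary outcome and cesarean by assigned arm are unaffected unless the score is used for adjustment.

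The size cannot be determined from the documents, because they give neither the share of late exams nor any sign of how scoring shifts. Under the one-directional assumptions shown, with 20% to 50% of exams late, the false RR for cesarean in the unfavorable group is about 0.98 to 0.93. If the moved women have intermediate risk it is about 0.99 to 0.97, with 0.99 to 0.91 in the favorable group. The distortion is negligible if few exams are late. It is material only if many are late and scoring shifts in one direction in one arm. The point is worth correcting because the correction is cheap, not because bias has been shown.

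**What to change.** Reconcile 4.1 and 4.2 so that all three score components are recorded within the 72 hours before randomization. Have AR02 and the randomization system require them before the assignment is released. The cost is small: 4.2 already has these women present in person for an exam that day, so only the order changes. A few exams will be done in women who are then not randomized.

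The last listed protocol change is dated July 2017 and the revised timetable ends enrollment in October 2017, so the reporting step matters more. For women already enrolled:

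- report by arm how many were examined after randomization, from the exam and randomization times;
- repeat the Bishop subgroup and interaction analysis on pre-randomization exams only, alongside the analysis of all women;
- do the same for any adjusted analysis that uses the score.

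The cost is a somewhat smaller subgroup in the sensitivity analysis.
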